5.1.4 Medical History

Medical history events are reported for the following Body Systems: Skin, Head-Eyes-Ears-Nose-Throat, Respiratory, Cardiovascular, Gastrointestinal, Endocrine/Metabolic, Genitourinary, Neurological, Blood/Lymphatic, Musculoskeletal, Hepatic, Allergies, Psychological/Psychiatric and Other. The medical history events will be summarized by Body System, Starting dose and overall.

Medical history data will be listed in a patient data listing.

5.1.5 **Prior and Concomitant Medications**

All medications will be coded according to the WHODRUG dictionary WHO-DDE-B2-June 2015.

The following prior medications will be summarized by Level 2 Classification and Preferred Name for each starting dose and overall:

- Previous corticosteroid medications taken and stopped prior to date of first study drug dosing
- Other medications taken and stopped prior to date of first study drug dosing

The following concomitant medications will be summarized by Level 2 Classification and Preferred Name for each dose level and overall:

- Corticosteroid medications taken during treatment
- Corticosteroid medications started after date of last study drug dosing
- Other medications taken on or after date of first study drug dosing

Medications will be attributed to the dose level where the medication is taken during the dose level. The same medication may be attributed to more than one dose level. Corticosteroid medication started after the date of last study drug dosing will be summarized separately.

Separate listings will be provided for prior corticosteroid treatment, concomitant corticosteroid medications, post last dose corticosteroid medications, other prior medications and other concomitant medications.

5.2 **Protocol Deviations**

Protocol deviations will be identified and classified into major vs. non-major by the Sponsor prior to database lock.

The major protocol deviations will be tabulated by the deviation categories, starting dose and overall for patients who are in the ITT population.

A patient data listing with deviation category and deviation details for both will be provided for the major protocol deviations and the non-major protocol deviations.

5.3 **Study Drug Treatment Exposure and Compliance**

Study drug treatment information will be summarized and documented in the ITT and mITT Population. Number of dose adjustments and maximum dose will be tabulated by starting dose. Descriptive statistics for study drug exposure and compliance will be done by dose level and overall. Patient data listings will be listed by starting dose and patient and study visit.

5.3.1 **Study Drug Exposure**

Study drug exposure will be summarized by dose level.

- Duration of exposure for Dose level i (days) =
(date of last dose for dose level i – date of first dose for dose level i) + 1.
- Dose Taken for Dose level i (mg) = (Number of tablets dispensed – Number of tablets returned)*
Current Dose Level (mg)
- Calculated Dose for Dose level i (mg/day) =
(Dose taken for Dose level i)/Duration of exposure for Dose level i.

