10 IDENTITY OF INVESTIGATIONAL PRODUCT

10.1 Formulation

Each PRN1008 film-coated tablet contains either 100 mg or 300 mg of PRN1008 drug substance. In addition, the tablet contains Microcrystalline Cellulose (filler), Crospovidone (disintegrant), Sodium Stearyl Fumarate (lubricant) and a non-functional film coating. The 100 mg tablet is a round shape and orange in color. The 300 mg tablet is an oval shape and white in color.

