2.2 Study Design

This is a Phase 2, open-label, pilot cohort study to evaluate the safety, clinical activity, pharmacodynamics, and pharmacodynamics of PRN1008 in patients with newly diagnosed or relapsing PV. An open-label design was chosen for several reasons: PV does not spontaneously remit so there is no placebo effect to account for; clinicians need to know when to use rescue CSs, if necessary, in a timely manner; and lastly, the pilot nature of the investigation itself is best explored in an open-label fashion.

Up to 28 days before enrollment in the study, patients will be required to sign an informed consent form, after which screening assessments will be carried out. Patients must fulfill all entry criteria to be enrolled into the study. Patients who fail to meet the entry criteria may be rescreened at the discretion of the Investigator. Up to 25 male or female patients with newly diagnosed (i.e., naïve to an effective induction treatment regimen) or relapsing, biopsy-proven, mild or moderate PV patients (Pemphigus Disease Activity Index [PDAI] 8 to 45) to enrolled into each parts of the study.

In Part A, the initial dosing was 400 mg twice daily (bid). The duration of study therapy was 12 weeks starting on Day 1 and ending on study Day 84 (total duration of individual subject participation is 28 weeks), with follow-up visits (off-treatment) until Week 29.

In Part B, the initial dosing is 400 mg once daily (qd), with intra-patient dose escalation to 400 mg bid allowed at or after the Week 3 visit for insufficient clinical response (and then again to 600 mg bid if necessary at or after the Week 5 visit). The duration of study therapy is 24 weeks starting on Day 1 and ending on study Day 169, with a follow-up visit (off-treatment) on Day 197 (Week 29). The total duration of individual subject participation is approximately 32 weeks.

Dose Escalation Rules Part B

Current Dose	Inadequate Clinical Response* Dose-Escalation Rules
400 mg qd	Increase to 400 mg bid (allowed at Week 3 visit or later)**
400 mg bid	Increase to 600 mg bid (allowed at Week 5 visit or later)**
600 mg bid	No dose increase possible.

* Investigator discretion: Generally, clinical response is shown by some improvement seen in first 2 weeks with CDA achieved by the Week 5 visit

** Unless tolerability issues preclude dose-escalation

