>=80 % and < 100 %	x (x.x)	x (x.x)	x (x.x)	x (x.x)
< 80%	x (x.x)	x (x.x)	x (x.x)	x (x.x)

The duration of exposure at each dose level is the date of last dose in a given dose level – date of first dose in the same dose level + 1.

The duration of exposure for “Overall” is date of last dose – date of first dose + 1.

Calculated dose in mg/day at each dose level = [Dose level (mg/day) x (Duration of exposure (x2 if BID) – doses missed)]/Duration of Exposure.

Compliance with study drug = the actual number of doses taken divided by the expected number of doses take, expressed as a percentage.

Program: <program name (date, time)>, Path: <path>

Table B.14.2.1.1.1 Proportion of patients Achieved CDA at or Prior to Week 5 without prednis(ol)one >0.5 mg/kg (mITT Population)

Achieved CDA at or Prior to Week 5 without prednis(ol)one >0.5 mg/kg	400 mg QD (N = n)	400 mg BID (N = n)	600 mg BID (N = n)	Overall (N = n)
N achieved (%)	x (x.x)	x (x.x)	x (x.x)	x (x.x)
- 80% CI	x.xx, x.xx	x.xx, x.xx	x.xx, x.xx	x.xx, x.xx
- 95% CI	x.xx, x.xx	x.xx, x.xx	x.xx, x.xx	x.xx, x.xx

Percentages are based on the number of patients in each dose group and overall.

Patients are classified into different dose levels according to the dose they received prior to achieving CDA.

Confidence Intervals are based on the Exact (Clopper-Pearson) method.

Primary efficacy endpoint: Proportion of patients who achieved CDA within 4 weeks of starting PRN1008 treatment, i.e. At or prior to Week 5, without prednis(ol)one equivalent > 0.5 mg/kg on the day prior to the assessment.

Program: <program name (date, time)>, Path: <path>

Table B.14.2.1.1.2 Proportion of patients Achieved CDA at or Prior to Week 5 without prednis(ol)one >0.5 mg/kg (Completer Population)

Table B.14.2.1.1.3 Proportion of patients Achieved CDA at or Prior to Week 5 without prednis(ol)one >0.5 mg/kg (PP Population)

Table B.14.2.1.2.1 Proportion of patients Achieved CDA at or Prior to Week 5 without prednis(ol)one >0.5 mg/kg – Subgroup – Age (mITT Population)

Subgroup	Achieved CDA at or Prior to Week 5 without prednis(ol)one >0.5 mg/kg	400 mg QD (N = n)	400 mg BID (N = n)	600 mg BID (N = n)	Overall (N = n)
Age < 50	Number of patients	n	n	n	n
	N achieved (%)	x (x.x)	x (x.x)	x (x.x)	x (x.x)
	- 80% CI	x.xx, x.xx	x.xx, x.xx	x.xx, x.xx	x.xx, x.xx
	- 95% CI	x.xx, x.xx	x.xx, x.xx	x.xx, x.xx	x.xx, x.xx
Age ≥ 50	Number of patients	n	n	n	n
	N achieved (%)	x (x.x)	x (x.x)	x (x.x)	x (x.x)

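### Part B SAP 5.3.1 multiplies tablet counts by dose level instead of tablet strength, overstating mg/day by the number of tablets per dose, and conflicts with the formula in its own table and listing

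*SAP*

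**What the plan says.** Part B SAP section 5.3.1 (Study Drug Exposure) sets out the calculation in two steps.

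- Dose taken: "Dose Taken for Dose level i (mg) = (Number of tablets dispensed" less tablets returned), multiplied by "Current Dose Level (mg").
- Calculated dose in mg/day: ("Dose taken for Dose level i)/Duration of exposure for Dose level i".

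The tablets are described in Protocol section 10.1: "Each PRN1008 film-coated tablet contains either 100 mg or 300 mg of PRN1008 drug substance". Part B SAP section 2.2 gives the dose levels. It says "In Part B, the initial dosing is 400 mg once daily (qd"), then allows the step "Increase to 400 mg bid (allowed at Week 3 visit or later"), and after that a step to 600 mg bid from Week 5.

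The shells that display this variable carry a different rule. The footnote to Table B.14.1.8.2, repeated under Listing B.16.2.5.2, begins "Calculated dose in mg/day at each dose level = [Dose level (mg/day) x (Duration of exposure (x2 if BID"). It then subtracts doses missed and divides by duration of exposure. Tablet counts do not appear in it.

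**The concern.** A count of tablets becomes milligrams only when each tablet is multiplied by its own strength. Section 5.3.1 multiplies by the dose level instead, and no available tablet is as large as any Part B dose level. The mg/day figure is the plan's summary of how much drug was actually taken at each level, in a part of the study meant to explore a lower starting dose. If 5.3.1 were programmed as it stands, that summary would be too high by a whole-number factor. The second formula for the same variable adds to the problem, because two programmers could each follow the SAP and obtain different values.

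**Working it through.** **Inputs.** Tablet strengths are 100 mg and 300 mg (Protocol 10.1). The dose levels are 400 mg qd, 400 mg bid and 600 mg bid (Part B SAP 2.2), that is 400, 800 and 1,200 mg/day. The number of tablets per dose is not stated and has to be assumed. The possible mixes are:

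- 400 mg: 300 + 100 (2 tablets) or 4 × 100 (4 tablets).
- 600 mg: 2 × 300 (2 tablets), 300 + 3 × 100 (4 tablets) or 6 × 100 (6 tablets).

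**Section 5.3.1.** Let k be tablets per dose, f doses per day, L mg per dose and D days. At full compliance the rule gives (k × f × D) × L / D = k × f × L. The true value is f × L. The ratio is therefore k, whatever the duration.

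For example, take 400 mg qd for 28 days with one 300 mg and one 100 mg tablet per dose. Tablets used are 2 × 28 = 56. The rule gives 56 × 400 / 28 = 800 mg/day. By strength it is (28 × 300 + 28 × 100) / 28 = 400 mg/day.

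| Dose level | True mg/day | 5.3.1, fewest tablets (k = 2) | 5.3.1, 100 mg tablets only |
|---|---|---|---|
| 400 mg qd | 400 | 800 | 1,600 (k = 4) |
| 400 mg bid | 800 | 1,600 | 3,200 (k = 4) |
| 600 mg bid | 1,200 | 2,400 | 7,200 (k = 6) |

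This reads the dose level as mg per dose, which fits the unit printed in 5.3.1. If it were read as mg/day, the bid ratios would double again (4 when k = 2).

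**Shell footnote, no missed doses.** The rule is level × (D × f) / D = level × f.

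| Dose level | Level read as mg per dose | Level read as mg/day, as labelled |
|---|---|---|
| 400 mg qd | 400 × 1 = 400 (correct) | 400 × 1 = 400 (correct) |
| 400 mg bid | 400 × 2 = 800 (correct) | 800 × 2 = 1,600 (double) |
| 600 mg bid | 600 × 2 = 1,200 (correct) | 1,200 × 2 = 2,400 (double) |

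**Tablet counts multiplied by strength.** Summing over strengths and dividing by days returns 400, 800 and 1,200 mg/day for every mix listed above.

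**The case against.** The strongest reply is that the results may never be computed from 5.3.1. The table and listing that present the variable print the missed-dose formula. Listing B.16.2.5.2 has a column for missed doses, Listing B.16.2.5.1 records their dates, and no Part B shell shows tablets dispensed or returned. The bracket in the footnote counts doses, so its natural multiplier is mg per dose, and on that reading it is right at every level. This stands. A reader might infer that the reported mg/day will be about double, or that the table will show doses above the 600 mg bid maximum. The documents do not support that: they show two conflicting formulas with no statement of precedence, and section 6 lets the shells be adjusted. Doubling of bid doses by the footnote depends on taking its 'mg/day' label literally. The two formulas are alternatives, so their errors do not compound.

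A reader might also infer that safety rates or the lower-dose comparison rest on this figure. They do not. Adverse event percentages use patient counts, with events assigned to the dose level at onset. Efficacy is tabulated by dose level received. Compliance in section 5.3.2 allows for the number of tablets per dose, so the 80% per-protocol criterion is unaffected.

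It can also be said that a mean near 800 mg/day under a 400 mg QD column would be noticed at once. Probably so, but that is a reason to correct the text before programming. Finally, the text of section 3.3 (Treatment Groups) was not available to check for a definition of dose level. Such a definition could settle the footnote's unit. It could not rescue 5.3.1, because neither mg per dose nor mg/day is a tablet strength.

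**Conclusion.** Section 5.3.1 is wrong as written. Followed literally at full compliance, it overstates mg/day by the number of tablets per dose: 2-fold at the least, and up to 4-fold for 400 mg or 6-fold for 600 mg if only 100 mg tablets are dispensed. The floor of 2 follows from the tablet strengths; the actual factor depends on a tablet mix that the documents do not give. The section also contradicts the footnotes to Table B.14.1.8.2 and Listing B.16.2.5.2, which are correct or double the bid levels according to how their unit label is read, and the SAP does not say which version governs. The consequence is limited to the descriptive exposure summary and one listing column. The primary endpoint, compliance, the per-protocol criterion and adverse event percentages do not use this variable.

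**What to change.** Choose one definition of calculated dose and print it identically in section 5.3.1, Table B.14.1.8.2 and Listing B.16.2.5.2.

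- Preferred: for each strength, (tablets dispensed − tablets returned) × strength (100 or 300 mg), summed over the two strengths and divided by days of exposure at that level.
- If Part B accountability is not held by strength: mg per dose × (scheduled doses − missed doses), divided by days of exposure, with the footnote's 'mg/day' label on dose level changed to 'mg per dose'.

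The Part A accountability shell (Listing 16.2.3.3) records counts by tablet strength. The Part B shells contain no such listing, so availability should be confirmed before the first option is chosen. The cost is a wording change and a small programming change; neither option adds data collection if the records it needs are already held.

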5.3.2 Study Drug Compliance

Compliance with study drug at each dose level and overall will be calculated as the actual number of doses taken divided by the expected number of doses to be taken (taking into account the # tablets for each dose), expressed as a percentage. Expected number of doses will be determined by the number of days in between visits and the frequency of dosing (QD or BID).

Compliance will be summarized by descriptive statistics for each dose level and overall. The number and percentage of patients with 100% compliance, greater than 80% but less than 100% compliance and less than 80% compliance will be tabulated for each dose level.

5.4 Efficacy Analyses

The mITT population will be used for all efficacy analyses. For analyses at a particular study drug dose, all patients who received that dose at least once will be included. In addition, for selected analyses, where specified, the Completer and PP population will be used.

The descriptive statistics will be done by dose level and overall for all study visits, unless specified otherwise. All binomial confidence intervals for efficacy analyses will use the Exact (Clopper-Pearson) method. Patient data listings will be listed by starting dose, patient, dose level and study visit.

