11.5.3 Efficacy Analysis Population

All patients who have received at least one dose of PRN1008 will be included in the efficacy analysis. Subject response and disease progression will be determined using PDAI, ABSIS, ABQOL, and TABQOL scores. Efficacy data will be presented in listings by subject and tabulated for each efficacy endpoint. Data may be combined where appropriate for Parts A

and B. Additional sub-group analyses (e.g. disease severity, dose group) may be performed as appropriate.

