3.2.3 Efficacy Analysis/Intent-to-Treat (ITT) Population

All patients who received at least one dose of PRN1008 in Part B will be included in the Efficacy/ITT analysis population.

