3.2.4 Modified Intent-to-Treat (mITT) Population

Patients treated up to Week 5 and had a Week 5 disease assessment will be included in the mITT population.

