5.4.1 Primary Efficacy Endpoint

The primary efficacy endpoint is:

- The proportion of patients who are able to achieve CDA within 4 weeks (on or prior to Week 5 visit) of starting PRN1008 treatment **without** the need for doses of prednis(ol)one > 0.5 mg/kg

The Control of Disease Activity (CDA) responses are assessed at visits specified in the Schedule of assessments (Table 1). Types of CS other than prednis(ol)one are converted to dose-equivalent prednis(ol)one (see Section 5.4.2.3).

This is operationalized as meaning the first CDA is achieved on or before the Week 5 visit but after first dose of PRN1008, and will be summarized, by dose level to the Week 5 visit and overall in a table, using frequencies and percentages. In addition, two-sided 80% and 95% CIs (Confidence Intervals) of the response rate will be provided for each dose level and overall.

Patients who are able to achieve CDA between first dose of study drug and the Week 5 visit without prednis(ol)one >0.5 mg/kg on the date prior to the CDA will be considered as responders, even if the CDA status was not maintained or higher doses of prednis(ol)one were used after the first CDA. Patients who are not able to achieve CDA prior to or at the Week 5 visit or had prednis(ol)one >0.5 mg/kg on the date prior to CDA will be considered as non-responders. Patients whose CDA status is unknown at the Week 5 visit for whatever reason (including early termination before Week 5 visit) will be also considered as non-responders. Only systemic CSs (as defined by medication taken orally or intravenously) are to be used to evaluate the efficacy endpoints, topical CSs (including buccal CS) will not be counted.

The number and percentage of patients who meet the primary efficacy endpoint criteria will be tabulated by dose level and overall (all patients).

A sensitivity analysis using the Completer and PP population will be provided.

Panel plots will be provided for PDAI score over the study period for each patient. Dose level (mg/day) will also be plotted on the same figure. Lines for the steroid equivalent dose in mg/kg will be added to the plots. A total of 9 plots (3 x 3) will be fitted on one page.

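### Part B SAP estimates the primary response rate only in patients treated to and assessed at Week 5, not in the protocol's all-dosed efficacy set, and Section 4.7 does not record the substitution

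*SAP*

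**What the plan says.** The protocol, Section 11.5.3: "All patients who have received at least one dose of PRN1008 will be included in the efficacy analysis". Part B SAP 3.2.3 keeps that rule: "All patients who received at least one dose of PRN1008 in Part B will be included in the Efficacy/ITT analysis population".

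Part B SAP 5.4 opens with a different set: "The mITT population will be used for all efficacy analyses". Section 3.2.4 defines it: "Patients treated up to Week 5 and had a Week 5 disease assessment will be included in the mITT population". For results by dose, 5.4 adds: "For analyses at a particular study drug dose, all patients who received that dose at least once will be included".

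Section 5.4.1 sets the scoring of the primary endpoint. Its non-responders include "Patients whose CDA status is unknown at the Week 5 visit for whatever reason (including early termination before Week 5 visit". Patients who reach CDA by Week 5 within the steroid limit "will be considered as responders, even if the CDA status was not maintained". Results "will be tabulated by dose level and overall (all patients". The only sensitivity sets named are Completer and PP.

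Section 4.7 lists mITT, Completer and PP as populations added to those in the protocol. The Part A SAP, Section 8, runs efficacy in ITT, mITT and PP.

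**The concern.** A rule that scores early termination as non-response needs a denominator that contains early terminators. In Part B the denominator removes them first. The primary rate is then conditional on staying on PRN1008 and being assessed to Week 5, and no planned table shows what that condition does.

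Losses before Week 5 need not be unrelated to response. Rescue Criteria #1 in protocol Appendix 1B, for example, stops PRN1008 for a flare judged potentially life-threatening. Section 2.3 says the sample size was chosen to give a point estimate of the primary endpoint and that the results will be used to design confirmatory trials, so the denominator of that estimate matters.

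**Working it through.** **Tracing one patient.** Take a patient dosed on Day 1 who leaves before the Week 5 visit.

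- Protocol 11.5.3 and SAP 3.2.3: in the efficacy set.
- SAP 5.4.1, if no CDA was recorded: non-responder.
- mITT (3.2.4): out.
- Completer (3.2.5) needs treatment to Week 25 and a Week 29 assessment: out.
- PP (3.2.6) needs the Week 29 visit: out.
- Tables B.14.2.1.1.1 to B.14.2.1.1.3 are mITT, Completer and PP, so the patient appears in no primary table.

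The rule is not entirely empty. Under 3.2.4 it could still reach a patient who had a Week 5 disease assessment with CDA status not recorded. The shells of Tables B.14.1.1.1 and B.14.1.1.4 ask for a Week 5 CDA assessment instead, and under that wording it reaches no one.

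**The plan's own figure.** Section 2.3 gives an 80% CI of ±13 points at a 50% rate with n = 25. Normal approximation: 1.2816 × √(0.5 × 0.5 / 25) = 0.128, or 12.8 points, which reproduces it. The exact (Clopper-Pearson) method named in 5.4 gives 37.5 to 66.2 at 13/25, a half-width of 14.4 points.

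**Size.** The number of dosed Part B patients outside mITT, k, is not given, so these are assumed values. Let R be the responders among 25 dosed, and r the number of those who are among the k excluded.

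- ITT rate = R / 25
- mITT rate = (R − r) / (25 − k)

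With R = 13, ITT = 13/25 = 52.0%.

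| k | r | mITT | mITT − ITT (points) |
|---|---|---|---|
| 0 | 0 | 13/25 = 52.0% | 0 |
| 1 | 0 | 13/24 = 54.2% | +2.2 |
| 3 | 0 | 13/22 = 59.1% (80% CI 43.2 to 73.6) | +7.1 |
| 5 | 0 | 13/20 = 65.0% (80% CI 48.2 to 79.3) | +13.0 |
| 3 | 1 | 12/22 = 54.5% | +2.5 |
| 3 | 2 | 11/22 = 50.0% | −2.0 |

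Rearranging, mITT exceeds ITT exactly when r/k is below R/25.

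**A conflict that ITT would expose.** A patient with documented CDA who leaves before Week 5 is a responder under one sentence of 5.4.1 (CDA need not be maintained) and a non-responder under another (status unknown at Week 5). Each such patient moves the ITT rate by 1/25 = 4.0 points. With mITT 12/22 = 54.5%, k = 3 and one such patient, ITT is 12/25 = 48.0% or 13/25 = 52.0%, depending on the sentence followed. Part A SAP 8.1 has the same two sentences. The programming note to Part A Table 14.2.1.1 scores early treatment terminators as non-responders.

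**The case against.** The strongest reply is that nothing is hidden or lost. Section 5.4 names mITT in its first sentence, 4.7 lists it with its section number, and the tables carry the population in their titles. Listing B.16.2.6.1 gives CDA status and date by visit for the ITT population. Listing B.16.2.6.10 gives steroid dose on the day before each visit alongside CDA and CR. A reader could rebuild an all-dosed rate from these. Part B is also a single-arm pilot with no hypothesis testing, and every upward shift shown above is smaller than the exact half-width of 14.4 points.

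Most of this is correct, and it limits the point. What remains is that no ITT summary or CI is planned, that a hand count would meet the unresolved conflict in 5.4.1, and that a shift from selection is not covered by a CI computed within the selected set.

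The phrases about all patients who received a dose, and about an overall column of all patients, might be read as restoring the all-dosed set. The table titles say mITT, so they do not, but the wording needs reconciling.

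One caution about the remedy stands. The text of Sections 3.2.8 (patients from Part A) and 3.3 (treatment groups) was not available for this review. Patients may continue from Part A mid-treatment, and the Week 5 rule could misclassify them if they sit in Part B ITT without special handling.

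**Conclusion.** The plan should be corrected. The Part B primary analysis departs from protocol 11.5.3 and from the SAP's own 3.2.3, and the early-termination part of the 5.4.1 rule has no one to act on. Section 4.7 discloses the addition of mITT but not that it replaces the all-dosed set for efficacy. The effect is zero if k is zero. It is +2.2 to +13.0 points for k from 1 to 5, assuming 25 dosed, 13 responders and no response among those excluded.

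Four stronger readings go beyond the documents:

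- *The mITT rate must be too high.* Only if the excluded patients respond less often than the all-dosed group; early CDA among them can reverse the sign.
- *Part B is already biased, as Part A's interim figures show.* Protocol 1.4.2.1 gives 11 of 18 (61.1%) with 21 dosed, and 11/21 would be 52.4%. But the other three may still have been on treatment, and those figures are not Part B data.
- *The all-dosed result cannot be recovered.* The ITT listings allow it by hand.
- *The secondary endpoints contain the same contradiction.* Section 5.4.2.1 has no non-responder rule for mITT to disable, so this is shown for the primary endpoint only.

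Confidence is high on the mismatch between sets. It is lower on the details of the remedy, because of the unseen roll-over provisions.

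**What to change.** 1. In 5.4 and 5.4.1, make ITT (at least one dose in Part B) the analysis set for the primary endpoint. Add an ITT version of Table B.14.2.1.1 with exact 80% and 95% CIs, and keep mITT as supportive. Part A already reports ITT.
2. In 4.7, record the departure from protocol 11.5.3 wherever efficacy stays in mITT. Reword the dose-level sentence in 5.4 and the overall column in 5.4.1 so that each names its analysis set.
3. In 5.4.1, state how a patient with documented CDA who leaves before Week 5 is counted. Use one rule for both Parts, checked against Part A SAP 8.1 and the note to Part A Table 14.2.1.1. If any such patient occurs, show the count both ways.
4. Apply to ITT whatever handling Sections 3.2.8 and 3.3 give to patients rolling over from Part A.

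ITT versions of the secondary CDA and CR tables are optional. The cost is an additional primary table from an existing population flag, plus SAP wording. The reported response rate may be lower.
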